8.6.3. Regulatory Reporting Requirements for Serious Adverse Events

The sponsor assumes responsibility for appropriate reporting of AEs to the regulatory authorities. The sponsor will also report to the investigator (and the head of the investigational institute where required) all suspected unexpected serious adverse reactions (SUSARs). The investigator (or sponsor where required) must report SUSARs to the appropriate IEC/IRB that approved the protocol unless otherwise required and documented by the IEC/IRB.

8.6.4. Pregnancy

All initial reports of pregnancy in female participants or partners of male participants must be reported to the sponsor by the study-site personnel within 24 hours of their knowledge of the event using the appropriate pregnancy notification form. Abnormal pregnancy outcomes (eg, spontaneous abortion, fetal death, stillbirth, congenital anomalies, ectopic pregnancy) are considered SAEs and must be reported using the Serious Adverse Event Form. If any participant becomes pregnant during the study, the study treatment should be suspended and the Medical Monitor should be contacted as soon as possible to discuss study treatment options.

Follow-up information regarding the outcome of the pregnancy and any postnatal sequelae in the infant will be required.

8.6.5. Adverse Events of Special Interest

Specific AEs or groups of AEs will be followed as part of standard safety monitoring activities by the sponsor. These events will be reported to the sponsor within 24 hours of awareness irrespective of seriousness (ie, SAEs and non-SAEs) following the procedure described above for SAEs and will require enhanced data collection.

Major Hemorrhage

Major hemorrhage is defined as any of the following:

1. Any treatment-emergent hemorrhagic AEs of \geq Grade 3 (Note: All hemorrhagic events requiring transfusion of red blood cells should be reported as \geq Grade 3 AE per NCI-CTCAE. Those events meeting the definition)
2. Any treatment-emergent SAEs of bleeding of any grade
3. Any treatment-emergent central nervous system hemorrhage/hematoma of any grade

Other Malignancies

In addition to all routine AE reporting; all new malignant tumors, including solid tumors, skin malignancies, and hematologic malignancies; are to be reported for the duration of study intervention and during any protocol-specified follow-up periods including postprogression follow-up for overall survival.

8.7. Treatment of Overdose

For this study, any dose of ibrutinib greater than 420 mg within a day will be considered an overdose. The sponsor does not recommend specific intervention for an overdose.

In the event of an overdose, the investigator or treating physician should:

- Contact the Medical Monitor immediately.
- Closely monitor the participant for AE/SAE and laboratory abnormalities until ibrutinib can no longer be detected systemically (at least 30 days).
- Obtain a plasma sample for PK analysis within 36 hours from the date of the last dose of study intervention if requested by the Medical Monitor (determined on a case-by-case basis).
- Document the quantity of the excess dose as well as the duration of the overdosing in the eCRF.

Decisions regarding dose interruptions or modifications will be made by the investigator in consultation with the Medical Monitor based on the clinical evaluation of the participant.

8.8. Pharmacokinetics

8.8.1. Evaluations

Blood samples of approximately 2 mL will be collected for measurement of plasma concentrations of ibrutinib and PCI-45227 (metabolite). Other potential metabolites of ibrutinib may be explored per the PK Sample Schedule ([Table 6](#)).

Samples collected for analyses of ibrutinib and PCI-45227 (metabolite) concentration may additionally be used to evaluate safety or efficacy aspects that address concerns arising during or after the study period for the evaluation of relevant biomarkers. Genetic analyses will not be performed on these plasma samples. Participant confidentiality will be maintained. Additional information about the collection, handling, and shipment of biological samples can be found in the laboratory manual.

8.8.2. Analytical Procedures

Pharmacokinetics

Plasma samples will be analyzed to determine concentrations of ibrutinib using a validated, specific, and sensitive liquid chromatography/tandem mass spectrometry method by or under the supervision of the sponsor. Other potential metabolites of ibrutinib may be explored ([Table 6](#)).

Table 6: Pharmacokinetic Sample Schedule

Week	Study Day	Predose	Timepoint Postdose ^a			
			1 h±15 min	2 h±15 min	4 h±30 min	6 h±1 h
4	1	X	X	X	X	X

^a Time after ibrutinib dosing

Refer to the laboratory manual for instructions on collecting and processing these samples. The participant should refrain from taking ibrutinib in the morning of study visits designated for the PK sampling. The investigator or designee will supervise administration of ibrutinib and the exact time of ibrutinib administration and blood samplings. Exact times of administration of study

intervention will be recorded. Predose sample will be collected 24 hours (± 2 hours) after dosing on the previous day and prior to dosing on the study day. Time of the last meal prior to the dosing to be recorded in the eCRF.

8.8.3. Pharmacokinetic Parameters and Evaluations

Parameters

At least following PK parameters for ibrutinib and PCI-45227 (metabolite) will be determined by noncompartment method. Predose concentrations will also be used as 24 hours concentrations for the PK parameters' calculation:

- Area under the plasma concentration-time curve from time zero to time of last measurable concentration (AUC_{last})
- Area under the plasma concentration-time curve from time zero to 24 hours (AUC_{24h})
- Maximum plasma concentration (C_{max})
- Time to reach the maximum plasma concentration (t_{max})
- Elimination half-life ($t_{1/2}$)

In addition, the plasma concentration data of ibrutinib may be used for population PK analysis.

8.9. Pharmacodynamics

Not applicable.

8.10. Biomarkers

Blood samples will be collected and used by sponsor for biomarker analysis. These biomarker analyses may include MYD88, CXCR-4, and other genetic and genomic alterations thought to be prognostic of disease and/or treatment outcomes.

A portion of pretreatment bone marrow samples collected for diagnosis may also be used by sponsor for further biomarker analysis.

Stopping Analysis

Biomarker analyses are dependent upon the availability of appropriate biomarker assays and clinical response rates. Biomarker analysis may be deferred or not performed, if during or at the end of the study, it becomes clear that the analysis will not have sufficient scientific value for biomarker evaluation, or if there are not enough samples or responders to allow for adequate biomarker evaluation. In the event the study is terminated early or shows poor clinical efficacy, completion of biomarker assessments is based on justification and intended utility of the data.

Additional Collections

If it is determined at any time before study completion that additional material is needed from a formalin-fixed, paraffin-embedded tumor sample for the successful completion of the protocol-specified analyses, the sponsor may request that additional material be retrieved from

existing samples. Also, based on emerging scientific evidence, the sponsor may request additional material from previously collected tumor samples during or after study completion for a retrospective analysis. In this case, such analyses would be specific to research related to the study intervention(s) or diseases being investigated.

9. STATISTICAL CONSIDERATIONS

Statistical analysis will be done by the sponsor or under the authority of the sponsor. A general description of the statistical methods to be used to analyze the efficacy and safety data is outlined below. Specific details will be provided in the statistical analysis plan (SAP).

A clinical cutoff for the primary analysis for all efficacy and safety endpoints will be conducted at the time when all participants complete the assessment of Week 57 or EOT visit. Final analysis will be conducted at the study end, when all the participants have completed all planned assessments or have discontinued the study.

9.1. Statistical Hypotheses

The primary hypothesis of this study is that ibrutinib in combination with rituximab is an effective agent in Japanese participants with treatment naïve or relapsed/refractory WM as measured by an ORR (the lower bound of exact 95% CI based on binomial distribution >32%).

9.2. Sample Size Determination

The target sample size is 14. Assuming an expected ORR of 72%, 14 participants are needed to demonstrate that the lower limit of exact 2-sided 95% CI of estimated ORR exceeds 32% with 80% power. The sample size was decided based on the study PCYC-1127-CA results, where the response rate was 72% for the ibrutinib plus rituximab arm, and 32% for the placebo plus rituximab arm.

9.3. Populations for Analyses

For purposes of analysis, the following populations are defined:

Population/Analysis Sets	Description
Enrolled	All participants who sign the ICF.
PK evaluable	All enrolled participants who will receive at least 1 dose of ibrutinib and have at least 1 postdose PK sample obtained.
Safety/ All treated	All enrolled participants who receive at least 1 dose of ibrutinib.
Response evaluable	All enrolled participants who have measurable disease at baseline, receive at least 1 dose of ibrutinib and who have at least 1 adequate postbaseline efficacy assessment.

9.4. Statistical Analyses

The SAP will be finalized prior to database lock and it will include a more technical and detailed description of the statistical analyses described in this section. This section is a summary of the planned statistical analyses of the most important endpoints including primary and key secondary endpoints.

9.4.1. General Considerations

For continuous variables, number of observations, means, standard deviations, medians, and ranges will be included. For categorical variables, frequency and percentage will be summarized. For time-to-event variables, Kaplan-Meier estimates will be provided.

All tests will be conducted at a 2-sided alpha level of 0.05, and 95% CIs will be provided, unless stated otherwise.

9.4.2. Primary Endpoint

Overall response rate is defined as the proportion of participants who achieve \geq PR according to the modified sixth IWWM (NCCN version 2, 2019).²⁷

Definition

Proportion of participants achieving a best overall response of confirmed CR, VGPR, or PR by IRC assessment at or prior to initiation of subsequent antineoplastic therapy.

Analysis Methods

The response evaluable analysis set will be used for primary endpoint. The all treated analysis set will be used for supplementary analysis.

The ORR and its 95% CI will be calculated with the exact test for binomial distribution in the response evaluable population. The study is considered to be positive if the lower limit of the exact 2-sided 95% CI based on binomial distribution exceeds the threshold value (0.32). Best overall response will also be summarized.

9.4.3. Secondary Endpoints

To evaluate efficacy of ibrutinib, when combined with rituximab in Japanese participants with treatment naïve or relapsed/refractory WM in terms of the following:

- Progression-free survival (PFS)
- Pharmacokinetics (PK) profile of ibrutinib and metabolite PCI-45227
- Prognostic biomarkers relative to disease and/or treatment outcomes including MYD88 and CXCR-4

Definition

PFS:

Time from the date of initial dose to the date of first documented evidence of PD, death, or date of censoring whichever occurs first, regardless of the use of subsequent antineoplastic therapy prior to documented PD or death [date of first PD or death or censoring date of initial dose+1 day]. Participants whose diseases have not progressed and who are still alive at the end of the study or clinical cutoff will be censored at the last adequate disease assessment. Participants who do not have any postbaseline disease evaluation will be censored at the date of the first dose of ibrutinib.

Analysis Methods

The all treated analysis set will be used for all secondary efficacy endpoints. The Kaplan-Meier method will be used to descriptively summarize the PFS in the all treated analysis set. Median PFS and the corresponding 95% CI will be provided if estimable with Kaplan-Meier plot.

In addition to the PK parameters described in Section 8.8.3, the plasma concentration data of ibrutinib may be used for population PK analysis. MYD88, CXCR-4, and other genetic and genomic alterations thought to be prognostic of disease and/or treatment outcome may be tested.

Safety evaluation is also a secondary endpoint for this study.

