- g. Women of childbearing potential only. Highly sensitive serum (β human chorionic gonadotropin [β hCG]) pregnancy test required at screening and urine pregnancy test required at Day 1 prior to first dose. If the test result is positive, the investigator should discuss with Medical Monitor and/or gynecologist and the pregnancy must be ruled out to be eligible.
- h. Participants who are positive for Hepatitis C antibody should have documented 24 weeks of sustained virologic response in order to be eligible for the study.
- i. Subsequent Serum viscosity (after screening) should be performed at the discretion of the treating physician in any participant with signs and symptoms suggesting a hyperviscosity syndrome.
- j. Repetitive serum immunofixation on study is only required to confirm a complete response (conducted on the first observation that the participant has no detectable monoclonal protein) and then repeated at every study visit until disease progression.
- k. Pharmacokinetic samples will be drawn for all participants according to the schedule in Section 8.8.2.
- l. These parameters will be used to assess possible tumor flare (IgM flare) after initiating treatment for safety observations.
- m. CT scans of the neck, chest, abdomen, and pelvis should be obtained during screening (up to 42 days before first dose) for each participant.
- n. Follow up CT scans should be performed at Week 57 for each participant. Other follow up CT scans will be required at Weeks 17, 33, 49, and every 24 weeks after Week 57 for all participants with measurable nodal/extranodal disease during screening. Additional assessments may be performed if clinically indicated during the course of the study at any time.
- o. CT scan at suspected PD visit may be performed if clinically indicated as reason for progression.
- p. Bone marrow aspirate and biopsy will be required at any time after screening to confirm a complete response. A clinical sample up to 60 days before first dose of ibrutinib can be used. A portion of these samples may be used for biomarker assessments.

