3. OBJECTIVES AND ENDPOINTS

Objectives	Endpoints
Primary	
 To evaluate ORR by IRC assessment, when combined with rituximab in Japanese participants with treatment naïve or relapsed/refractory WM. The ORR is defined as the proportion of participants with CR, VGPR, or PR (ie, \geqPR) by IRC assessment. Response will be defined by the modified sixth IWWM (NCCN version 2, 2019).²⁷
Secondary	
 To assess PFS by IRC assessment. PFS is defined as duration from the date of initial dose of ibrutinib to the date of disease progression or death, whichever occurs first. To determine the PK of ibrutinib in combination with rituximab in Japanese participants with treatment naïve or relapsed/refractory WM. PK parameters of ibrutinib and metabolite PCI-45227 (if possible and judged relevant). To explore biomarkers identified from other studies of ibrutinib in samples collected for MYD88 and CXCR-4 assessments. Prognostic biomarkers relative to disease and/or treatment outcomes including MYD88 and CXCR-4. To evaluate safety of ibrutinib, when combined with rituximab in Japanese participants with treatment naïve or relapsed/refractory WM. Safety parameters of ibrutinib, including AEs and clinical laboratory assessments.

Keys: AE adverse event; CR complete response; CXCR 4 C X C chemokine receptor type 4; IRC independent review committee; IWWM International Workshop on Waldenstrom's Macroglobulinemia; MYD88 myeloid differentiation primary response gene 88; NCCN National Comprehensive Cancer Network; ORR overall response rate; PFS progression free survival; PK pharmacokinetics; PR partial response; VGPR very good partial response; WM Waldenstrom's Macroglobulinemia.

Refer to Section 8, Study Assessments and Procedures for evaluations related to endpoints.

HYPOTHESIS

The primary hypothesis of this study is that ibrutinib in combination with rituximab is an effective agent in Japanese participants with treatment naïve or relapsed/refractory WM as measured by an ORR (the lower bound of exact 95% CI based on binomial distribution $>32\%$).

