8.2.8. Suspected PD Visit

The suspected PD visit should be performed at any time during the study, if based on clinical and/or laboratory evaluation, the investigator suspects PD, or if the participant discontinues treatment for any other reason. If possible, the visit should be performed within 24 hours after the participant's previous dose. The following procedures will be performed:

- Complete physical examination including general appearance of the participant, weight, and examination per clinical practice
- ECOG performance status
- Vitals signs (including blood pressure, pulse rate, respiratory rate, and body temperature)
- Collect blood samples for the following laboratory tests:
 - Hematology
 - Serum chemistry
 - Serum protein electrophoresis (SPEP)
 - Quantitative serum IgS (IgA, IgG, and IgM)

- Imaging by CT scan may be performed if clinically indicated as reason for progression
- Overall disease assessment
- Review of AEs and concomitant medications

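### As written, the PFS censoring rule removes a death that occurs before any postbaseline disease evaluation

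*Protocol*

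**What the plan says.** Section 3 (and the synopsis) defines the endpoint: "PFS is defined as duration from the date of initial dose of ibrutinib to the date of disease progression or death, whichever occurs first". A death needs no earlier assessment to count.

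Section 9.4.3 makes this operational. Time runs to the "date of first documented evidence of PD, death, or date of censoring whichever occurs first". Two censoring rules follow:

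- Rule 1: "Participants whose diseases have not progressed and who are still alive at the end of the study or clinical cutoff will be censored", with the last adequate disease assessment as the censoring date.
- Rule 2: "Participants who do not have any postbaseline disease evaluation will be censored at the date of the first dose of ibrutinib".

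PFS is analysed in the all treated set, which Section 9.3 defines by receipt of at least one dose of ibrutinib. A participant who dies early without an assessment is therefore in the PFS analysis.

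**The concern.** Rule 1 applies only to participants who are alive and have not progressed. Rule 2 carries neither condition and nothing in the protocol ranks death above it. Applied literally, it turns a death before the first disease evaluation into a censored observation of minimal length. The endpoint definition in Section 3 would count the same death as an event.

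The censoring is also informative, because the death is the reason no evaluation exists. Each affected death drops out of the Kaplan-Meier estimate, so the bias can only raise reported PFS. In a study of 14, one participant is 7.1 percentage points.

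**Working it through.** **Step 1. Apply the rules to one participant.** Suppose a participant takes ibrutinib on Day 1 and dies on Day 20 of a cause other than progression, with no disease evaluation after baseline.

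| Text | Result |
|---|---|
| Section 3 definition | Event on Day 20 |
| Section 9.4.3, Rule 1 | Does not apply (not alive) |
| Section 9.4.3, Rule 2 | Applies; censoring date is Day 1 |
| Section 9.4.3, earliest of PD, death, censoring | Day 1 precedes Day 20, so censored |

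**Step 2. Who is exposed.** The first scheduled overall disease assessment is at Week 5 (Section 8.2.3), so the window is roughly the first four weeks. Two things may shorten it:

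- Section 8.2.8 allows an earlier evaluation: "The suspected PD visit should be performed at any time during the study".
- IgM is drawn at Weeks 2 to 4. Whether those draws count as disease evaluations is unclear, because footnote l of the Schedule of Activities says: "These parameters will be used to assess possible tumor flare (IgM flare) after initiating treatment for safety observations".

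Delayed or remote visits under Appendix 10 could lengthen it. Section 2.3.1 describes fatal arrhythmias, fatal bleeding and infections associated with death, so a non-progression death in the window is possible.

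**Step 3. Size of the effect on PFS.** The protocol gives no early-death rate. Assume one such death among 14 treated, then *k* later events among the other 13, with no other censoring.

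- As written (censored on Day 1): S = (13 − k)/13
- Death counted: S = (13 − k)/14
- Gap: (13 − k)/13 − (13 − k)/14 = (13 − k)/182

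| k | As written | Death counted | Gap |
|---|---|---|---|
| 0 | 100% | 92.9% | 7.1 points |
| 3 | 76.9% | 71.4% | 5.5 points |
| 6 | 53.8% | 50.0% | 3.8 points |

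For 13/14, the Greenwood term is 1/(14 × 13) = 1/182, and the log-log 95% CI is 59.1% to 99.0%.

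The k = 6 row touches a planned output, median PFS. Take the median as the first time the estimate is at or below 50%. With the death counted, that is the sixth later event. As written, it is the seventh (6/13 = 46.2%).

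**Step 4. How likely is at least one such death?** With 14 participants and an assumed individual risk *p*, the chance is 1 − (1 − p)^14: 13% at p = 1%, 25% at p = 2% and 51% at p = 5%. These risks are illustrative.

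**Step 5. The primary endpoint does not move.** The only stated design figure is for ORR, and it reproduces. With N = 14, 9 responders are needed (Clopper-Pearson lower limit 0.351 against 0.32) and exact power at an ORR of 72% is 82.8%, against the 80% stated. If the early death leaves 13 response evaluable participants, 9 responders are still needed:

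| Responders | Lower limit, n = 13 | Lower limit, n = 14 |
|---|---|---|
| 8 | 0.316 (fail) | 0.289 (fail) |
| 9 | 0.386 (pass) | 0.351 (pass) |

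Section 9.4.2 adds: "The all treated analysis set will be used for supplementary analysis". There the participant remains in the denominator as a non-responder.

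**The case against.** The strongest reply is that Rule 2 is only a fallback to Rule 1. Rule 1 assigns the last adequate assessment, and Rule 2 supplies a date when none exists, so it inherits the progression-free and alive conditions. On that reading, a censoring date matters only for someone who is already censored, and appealing to the earliest-date clause assumes what is in dispute. This reading is possible and is probably what was intended. However, the protocol does not state it, and the condition appears in one sentence and is missing from the next.

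A second reply is that Section 9 leaves detail to the SAP, which was not among the documents reviewed. That would answer a missing rule. Here the protocol writes the rule itself, and an SAP that elaborates it faithfully would carry the fault forward.

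A third is that Section 4.1 treats death due to progression as an adequate assessment. That clause belongs to the response evaluable population for ORR. Even if carried over to PFS, it would not cover deaths from other causes.

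What stands is the point about scale. If the IgM draws at Weeks 2 to 4 count as evaluations, the window shrinks to about the first week. PFS has no test or success threshold, the 7.1-point gap is small beside the 59.1% to 99.0% interval, and an early death would still appear in the safety reporting.

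**Conclusion.** The concern holds. Read as written, Section 9.4.3 censors at first dose a participant who dies before any postbaseline disease evaluation, which contradicts the endpoint definition in Section 3. The distortion always favours treatment. On the assumption of a single such death among 14, with no censoring among the others, it is 7.1 points with no later events, falling to 3.8 points with six. The triggering event is uncommon and its probability cannot be taken from the protocol. The consequence is confined to a descriptive secondary summary. The correction should be made, but the design and the primary conclusion do not depend on it.

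**What to change.** Replace Rule 2 with wording to this effect: *A participant who is alive and has had no disease evaluation since baseline is censored on the day of the first ibrutinib dose. A death with no earlier disease evaluation is a PFS event on the day of death.*

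Keep the censoring date in the PFS time definition, and add a clause that it applies only to participants with neither progression nor death.

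The cost is one sentence and one clause, with no change to data collection, sample size or the primary analysis. Making the change before the data are examined avoids having to decide afterwards how to classify an individual death in a small open-label study.
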